11.1 Endpoint Analysis

Since the objective of this feasibility study is to characterize the performance of LITT, no formal hypotheses tests are planned for any endpoint. Descriptive statistics and exploratory analyses will be used in reporting outcomes for all endpoints.

11.1.1 Primary Endpoint: Analysis of Adverse Events

Adverse events will be presented in summary tables displaying the number of events, the number of enrolled subjects with ≥ 1 event, and the proportion of enrolled subjects with ≥ 1 event. The rates of adverse events will serve as the primary analysis.

Adverse event analysis may be repeated for only those events that occur after the initiation of treatment with rates calculated as a proportion of treated subjects..

Phase

The timing of adverse events relative to the initial LITT procedure will be tabulated by reporting the event counts, subject counts, and subject rates of events that occur within the following phases:

- **Baseline:** Prior to LITT procedure
- **Operative:** From the beginning of the LITT procedure through 30 days post-procedure
- **Year 1:** From 31 days post-procedure through 12 study months (12 month visit date or close of 12 month visit window if 12 month visit is missed)
- **Year 2:** After 12 study months through 24 study months (24 month visit date or close of 24 month visit window if 24 month visit is missed)

Additional analyses may be performed that divide the above phases into more detailed time intervals or that combine phases to present an overall summary of all adverse events through a specific time point (e.g. Operative Through Year 2).

Severity

The severity of adverse events will be tabulated by reporting the event counts, subject counts, and subject rates of events that are:

- **Mild:** Does not interfere in a significant manner with the subject's normal functioning level.
- **Moderate:** Produces some impairment of functioning but is not hazardous to health.
- **Severe:** Produces significant impairment of function or incapacitation and is a hazard to the subject's health.

Relationship

The relationship of adverse events to the device treatment or procedure will be tabulated by reporting the event counts, subject counts, and subject rates of events based on the following relationship categories:

- **Definite** – The adverse event follows a strong temporal sequence to the receipt (or attempted receipt) of the device treatment or procedure. This can include an adverse event that occurs after the study procedure.
- **Probable** – The adverse event follows a reasonable temporal sequence to the receipt (or attempted receipt) of the device treatment or procedure, and the possibilities of other factors, such as underlying and concomitant illness, concomitant medications, or concurrent treatment can be excluded.
- **Possible** – The adverse event follows a reasonable temporal sequence from receipt of the device treatment or procedure and the possibility of device treatment or procedure involvement cannot be excluded. However, other factors such as underlying or concomitant illness, concomitant medications, or concurrent treatment are presumable.
- **Unlikely** – The adverse event has an improbable temporal sequence to the receipt of the device treatment or procedure, or it can be reasonably explained by other factors, including underlying or concomitant illness, concomitant medications, or concurrent treatment.
- **Not Related** – The adverse event has no temporal sequence to the LITT procedure, NeuroBlate System or any user handling, or it can be explained by other factors, including underlying disease or concomitant illness, concomitant medication, or concurrent treatment.

In addition, the relationship may be characterized in a binary way as Related or Unrelated where Related corresponds to the categories Definite, Probable, Possible and Unrelated corresponds to the categories Unlikely, Not Related.

For events that are Unrelated to the device treatment or procedure, the relationship to the following factors will be tabulated:

- **New illness or injury:** Event is clearly attributable to a new illness or injury with no temporal relationship to the device, procedure, treatment or a medication.
- **Pre-existing condition/disease:** Event is attributable to an underlying condition/disease with no temporal relationship to the device, procedure, treatment or medication.
- **Epilepsy medication:** Event has a strong temporal relationship to an epilepsy medication.
- **Medication (non-epilepsy):** Event has a strong temporal relationship to a non-epilepsy medication.
- **Anesthesia:** Event has a strong temporal relationship to anesthesia.
- **Other:** Event has a relationship to another potential causation
- **Unknown:** Event relationship is not known or unsure.

Sets of Events

The tabulation of event type and cross-tabulation of event type by severity and relationship will be repeated, at a minimum, for the following sets of events:

- All Adverse Events (AEs)
- Serious Adverse Events (SAEs)
- Adverse Device Effects (i.e. AEs related to the use of the study device. This will include any event that is assessed as definitely, probably or possibly related to the device or the LITT procedure)
- Serious Adverse Device Effects (SADEs)
- Unanticipated Adverse Device Effect (UADE) / Unanticipated Serious Adverse Device Effect (USADE)

If any of the sets of events above does not occur in the study, that will be noted and no tabulation is required for that set.

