7.7 Additional LITT Procedure(s)

If a subject undergoes an additional LITT MTLE procedure for persistent seizures, the following evaluations and CRFs will be completed:

- *Neuropsychological Testing* CRF (testing must be completed prior to the procedure)
- Evaluation CRF (for an unscheduled (Discharge) visit)
- LITT Procedure CRF

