12.3 Duration variables

Months for this study are defined as 28-day intervals and are referred to as "study months" to distinguish the interval from calendar months. Duration in study months is calculated as the number of days divided by 28. Duration in study years is calculated as the number of days divided by 12 study months.

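### Adverse-event phases run from the first LITT only, so acute events of a repeat LITT fall into the Year 1 and Year 2 rows and no 30-day risk is reported for repeat procedures

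*SAP*

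**What the plan says.** SAP 11.1.1 (Phase) sets the time origin: "The timing of adverse events relative to the initial LITT procedure will be tabulated". The Operative phase is defined as "From the beginning of the LITT procedure through 30 days post-procedure", Year 1 as "From 31 days post-procedure through 12 study months" and Year 2 as "After 12 study months through 24 study months". Each row carries event counts, subject counts and subject rates. SAP 12.3 adds "Months for this study are defined as 28-day intervals", so 12 study months are nominally 336 days. In practice Year 1 closes at the 12-month visit, or at the end of that visit's window if the visit is missed.

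Protocol 7.7 provides for repeats: "If a subject undergoes an additional LITT MTLE procedure for persistent seizures, the following evaluations and CRFs will be completed". The list includes a LITT Procedure CRF. Protocol 9.1 and 9.2 collect adverse events from the day of the procedure to the end of participation, so events after a repeat LITT are in the data.

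SAP 11.1.1 names the adverse-event rates as the primary analysis, with enrolled subjects as denominator, and allows a repeat analysis on treated subjects. SAP section 9 plans about 30 treated subjects from up to 45 enrolled.

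**The concern.** Safety of LITT is the primary endpoint, and the phase table is where a reader will separate acute procedural risk from what happens later. The Year 1 and Year 2 rows look like the later part. If a subject has a second LITT in month 8 and a haemorrhage that day, the event appears under Year 1 with nothing in the table to show that it was perioperative. At the same time, the plan produces no 30-day event rate for repeat procedures. SAP section 9 says the results should help plan a larger pivotal trial, and that rate would be useful there. With about 30 treated subjects, one event can change how a row reads.

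**Working it through.** **The plan's own figure.** SAP section 9 says an event with 5% per-subject probability has about an 80% chance of being seen at least once in 30 subjects. 1 − 0.95^30 = 0.785, which agrees. The figure is not in dispute. It shows that the study is sized around seeing single events.

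**Applying the phase rule.** Take the first LITT as day 0 and the end of Year 1 as day 12 × 28 = 336. Compare the SAP rule with a rule that treats days 0 to 30 after any LITT as operative.

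| Repeat LITT on day | Event on day | SAP phase | Within 30 days of a LITT? |
|---|---|---|---|
| 20 | 20, 25 | Operative | yes |
| 20 | 50 | Year 1 | yes |
| 180 | 180, 185, 210 | Year 1 | yes |
| 336 | 336 | Year 1 | yes |
| 336 | 341, 366 | Year 2 | yes |
| 400 | 400, 405, 430 | Year 2 | yes |

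For any repeat on day 31 or later, the whole 30-day window lies outside Operative. For an earlier repeat, only the part after day 30 does. A repeat near the 12-month boundary has its window split between Year 1 and Year 2.

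**Looking for a correction elsewhere.**
- The optional extra phase analyses in SAP 11.1.1 divide or combine the same phases and keep the same origin.
- The relationship and device-effect tables show that an event is related, but not which procedure it followed.
- Repeat LITT is neither a subgroup (SAP section 13) nor a listed treatment factor (SAP section 14).
- SAP 18.1 item 2 is a sensitivity analysis that excludes visits after a change in other concomitant epilepsy treatment. It does not re-anchor adverse-event phases.

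**Size.** The documents give neither the number of repeats (m) nor the 30-day risk per procedure (q). Assumptions: 30 treated subjects; m of them have one repeat each, after day 30; q is the same at each procedure; procedures are independent.

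- Expected subjects with an acute event after a repeat, filed in Year 1 or Year 2: m × q. With q = 0.30 this is 2 × 0.30 = 0.6 to 5 × 0.30 = 1.5 subjects.
- Operative subject rate under the SAP rule: q.
- Subject rate for an operative event after any LITT: [(30 − m)q + m(1 − (1 − q)²)] / 30 = q + m·q(1 − q)/30.
- Difference: m·q(1 − q)/30.

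| q | m = 2 | m = 5 |
|---|---|---|
| 0.30 | 2 × 0.30 × 0.70 / 30 = 1.4 points | 5 × 0.30 × 0.70 / 30 = 3.5 points |
| 0.10 | 2 × 0.10 × 0.90 / 30 = 0.6 points | 5 × 0.10 × 0.90 / 30 = 1.5 points |

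With 45 enrolled subjects as denominator, the q = 0.30 line becomes 0.42/45 = 0.9 to 1.05/45 = 2.3 points. With m = 0 every difference is zero.

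**The case against.** The SAP discloses its time origin. Against that definition a month 8 event belongs in Year 1, and the SAP describes Year 1 and Year 2 as time intervals, not as late effects. All of this stands, and it rules out three stronger readings.

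- A reader might infer that the Operative row understates operative risk. It does not. It estimates 30-day risk after the first LITT, one exposure per subject, and events of a repeat do not bias that quantity. The understatement would exist only if the row were meant to cover any LITT, which the SAP does not say.
- A reader might infer that the primary safety results are wrong. The primary analysis is the overall adverse-event rate, which has no phase split, and Protocol 10.1.1 contains no phase table at all. The severity and relationship tables and the sets of serious and device-related events do not depend on phase. The event is counted in every one that applies to it, and the listings show both committee and investigator categories (SAP 15.3).
- A reader might put the shift in the operative subject rate at m × 0.30 / 30, or 2 to 5 points. That counts again those subjects who already had an operative event after the first LITT. Removing them gives 1.4 to 3.5 points.

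The SAP also cites protocol Rev A, while the protocol supplied is Rev B, so it cannot be checked whether section 7.7 was there when the SAP was written. This carries little weight, because the SAP's reference to the initial procedure suggests that later ones were expected. SAP section 1 permits ad hoc analyses, but a table chosen after the events are known is weaker than one specified beforehand.

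**Conclusion.** The point holds in a limited form. The later phase rows combine acute events of any repeat LITT done after day 30 with events remote from any procedure, and no repeat-procedure risk is planned. The events are misplaced in time within one descriptive table; they are not lost. The 1.4 to 3.5 points rest on the assumed 2 to 5 repeats and 30% risk. They fall with a lower risk or the enrolled denominator, and vanish if nobody has a second LITT. This is a cheap improvement and does not threaten the primary analysis.

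**What to change.** In SAP 11.1.1:

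1. Keep the Operative phase as it is and label it as the initial LITT.
2. Add a Repeat operative row, from the start of any additional LITT through 30 days after it, with event counts, subject counts and a rate per repeat procedure.
3. Limit Year 1 and Year 2 to events outside any 30-day operative window.
4. State which row takes an event that falls in both windows when a repeat follows within 30 days of the first LITT, so that nothing is counted twice.

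The cost is one more row, a second denominator and revised wording for two phases. The repeat row will rest on few procedures, so counts should be shown beside the rate. New data collection should not be needed: Protocol 7.7 requires a LITT Procedure CRF for each repeat, and Protocol 12.4.2 requires sites to record when the device was used. The CRF fields are not shown, so it should be confirmed that the form carries the procedure date.

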7.6.2 LITT Procedure

An MRI will be performed prior to surgery to determine trajectory and frame/arc settings. The LITT procedure will be performed per the IFU. Adverse events that occur during the procedure will be collected.

Postoperatively, the subject should be managed per the institution's standard of care for subjects receiving LITT. This includes monitoring of the subject's neurological status as it relates to possible intraoperative or postoperative adverse events (including intracranial hemorrhage).

Subjects experiencing a failed LITT treatment attempt (stopping the procedure prior to thermal delivery) will be followed for 1 month post-procedure for adverse events.

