7.8 Early Withdrawal/Premature Discontinuation of Subjects

Subjects may be withdrawn early from the study for a number of reasons, including:

- Subjects experiencing a failed LITT treatment attempt. A failed LITT treatment attempt is defined as stopping the procedure prior to thermal delivery. (Subjects that experience a failed treatment attempt will be followed for 1 month post-procedure for related adverse events.)
- Subject death
- Subject lost to follow-up
- Subject request for withdrawal
- Adverse events
- Investigator decision (other than an adverse event)

If a study subject is discontinued from the study early, a Study Completion CRF must be completed describing the reason for early discontinuation. The investigator should make all attempts to conduct an Early Withdrawal visit at the time of withdrawal from the study. If a subject has withdrawn consent for the study or is lost to follow-up, the completion of this visit is not imperative. In situations where study withdrawal is due to an adverse event, subjects will be followed until resolution of the adverse event or determination that the subject's condition is stable.

At the Early Withdrawal visit, the subject will undergo the following evaluations:

- QOLIE-31. It is preferred that the subject completes the questionnaire prior to any other tests.
- Neurological exam (cranial nerves (including confrontation visual field testing), motor, coordination, reflexes, gait, sensation)
- Neuropsychological testing
- Adverse event monitoring
- Subject satisfaction
- Functional assessment (including employment status, education, living arrangements, driving status)
- Surgical outcome classifications (Engel and ILAE, see Appendix D)

If a subject chooses to withdraw from the study and also withdraws consent for disclosure of future information, no further evaluation(s) should be performed and no additional data will be collected. The Sponsor may retain and continue to use any data collected prior to the withdrawal of consent.

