10.1.1 Primary Endpoint: Analysis of Adverse Events

For adverse events, both event counts and counts of subjects experiencing those events will be reported in tabular summaries. Rates will be reported based on the number of subjects experiencing one or more event as a proportion of all enrolled subjects and these subject rates will serve as the primary analysis.

Adverse event analysis may be repeated for events that occur after the initiation of treatment with rates calculated as a proportion of treated subjects, if it occurs that not all enrolled subjects undergo treatment with LITT.

Event counts, subject counts, and subject rates will also be reported for the following subsets of adverse events: SAE, SADE, UADE, USADE. Adverse events will be further characterized by tabulating the event severity and relationship (see section 9.1).

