12.4 Rate variables

Rates will be calculated as the ratio of the number of events divided by the number of days over which data collection occurred. Rates may be reported as events per day, per study month, or per study year. For diary data, days on which episode data is not available will not be included in the denominator.

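### Year 1 and Year 2 adverse-event rates keep subjects in the denominator after their observation has ended, so the later-phase rates are understated

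*SAP*

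**What the plan says.** Protocol 10.1.1 defines the primary adverse-event measure: "Rates will be reported based on the number of subjects experiencing one or more event as a proportion of all enrolled subjects". It calls these subject rates. SAP 11.1.1 uses the same denominator, "the proportion of enrolled subjects with ≥ 1 event", and allows an optional repeat for events after the start of treatment, "with rates calculated as a proportion of treated subjects".

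The Phase paragraph of SAP 11.1.1 then has event timing "tabulated by reporting the event counts, subject counts, and subject rates of events that occur within the following phases". The post-procedure phases are Operative (through 30 days), Year 1 (day 31 through 12 study months) and Year 2 (after 12 through 24 study months). Year 2 closes at the "24 month visit date or close of 24 month visit window if 24 month visit is missed". That covers a missed visit but not a subject who has already left. The paragraph gives no phase-specific denominator, number at risk or censoring rule.

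Two protocol sections describe observation that ends early. Under 7.6.2, subjects whose procedure is stopped before thermal delivery "will be followed for 1 month post-procedure for adverse events". Under 7.8, subjects may leave through death, loss to follow-up, request, adverse event or investigator decision. If a subject also withdraws consent to disclosure of future information, "no further evaluation(s) should be performed and no additional data will be collected".

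SAP 12.4 gives a general rule: "Rates will be calculated as the ratio of the number of events divided by the number of days over which data collection occurred".

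**The concern.** A subject rate for Year 2 should describe subjects who could have had a Year 2 event recorded. With a fixed denominator, a subject who left at Month 9 is counted as event-free for all of Year 2.

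Safety is the primary endpoint, and the phase table is where a reader will look to see whether harm persists or fades. SAP section 9 says the results should permit planning of a pivotal trial, so a diluted late rate would carry over into that planning.

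The SAP deals with incomplete follow-up elsewhere. In 11.1.3, Engel and ILAE classes are tabulated among subjects who complete the visit. Seizure freedom uses Kaplan-Meier with censoring at the last completed diary date, and rescue-medication use follows the same methods. The adverse-event phase tables have no equivalent.

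**Working it through.** **Inputs from the documents.** About 30 treated subjects (protocol 6.1; SAP section 9). Up to 45 enrolled (SAP section 9 only; the SAP cites protocol Rev A, and Rev B gives no such number). A study month is 28 days (SAP 12.3).

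**Assumptions.** Loss d of 10%, 20% or 30% by Month 24, and a true phase risk p of 20%. Loss is unrelated to adverse-event risk.

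**The plan's own figure.** The chance that a 5% event is seen at least once in 30 subjects is 1 − 0.95^30 = 78.5%, which agrees with the stated figure of about 80%. With 27, 24 or 21 subjects under observation it becomes 75.0%, 70.8% or 65.9%.

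**Case A: all losses before Year 2.** Reported rate = p × (number observed / fixed denominator).

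| Loss | Observed | Per 30 treated | Per 45 enrolled | Per number observed |
|---|---|---|---|---|
| 0% | 30 | 20.0% | 13.3% | 20% |
| 10% | 27 | 18.0% | 12.0% | 20% |
| 20% | 24 | 16.0% | 10.7% | 20% |
| 30% | 21 | 14.0% | 9.3% | 20% |

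The enrolled column uses the SAP ceiling. There, subjects who never received thermal delivery alone multiply the rate by 30/45 = 0.667.

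**Case B: losses spread evenly over 24 study months.** For a phase from month a to month b with constant hazard λ = −ln(1 − p)/(b − a), the reported rate on the treated denominator is

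p(1 − d·b/24) + (d/24)·[(b − a) − p/λ].

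For Year 2 with d = 10%: λ = 0.2231/12 = 0.01860 and p/λ = 10.755, so the rate is 0.2 × 0.9 + (0.1/24) × 1.245 = 0.180 + 0.0052 = 18.5%. Year 1 uses a = 31/28 and b = 12. The last column divides the Year 2 rate by the share present at the start of Year 2, which is 1 − d/2.

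| Loss | Year 1, treated | Year 2, treated | Year 2, phase-start denominator |
|---|---|---|---|
| 10% | 19.5% | 18.5% | 19.5% |
| 20% | 18.9% | 17.0% | 18.9% |
| 30% | 18.4% | 15.6% | 18.3% |

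Year 1 is affected little and Year 2 more. A phase-start denominator recovers most of the shortfall. The residual comes from subjects who leave within the phase, and person-time removes it under these assumptions.

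**Phase length.** Year 1 lasts 336 − 30 = 306 days and Year 2 lasts 336 days. Case B sets the risk at 20% in each phase. If instead the daily hazard is constant and gives 20% in Year 2, the true Year 1 risk is 1 − 0.8^(306/336) = 18.4%. The same formula, in days, then gives Year 1 as 17.9%, 17.4% and 16.9%, against Year 2 at 18.5%, 17.0% and 15.6%.

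**Scale against sampling error.** Five subjects with an event are 5/30 = 16.7% (Clopper-Pearson 95% interval 5.6% to 34.7%) on all treated, and 5/24 = 20.8% (7.1% to 42.2%) on those observed.

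**The case against.** **The consequence is small.** The study is single-arm and descriptive, with no hypothesis tests. The phase table is a breakdown of the primary rates, and a fixed-denominator proportion is a conventional display. At light loss the shift is well inside the sampling interval. This stands and limits the weight of the point. It does not remove it, because sampling error has no preferred direction and this error always points downward.

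**A reader could correct the rates.** Event and subject counts are printed beside them, SAP 12.2 reports visit completions and exits, and SAP section 17 reports compliance and reasons for withdrawal. That allows an approximation, but visit counts do not give person-time and the printed rate stays diluted.

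**Other SAP sections cover it.** SAP 12.4 divides events by days observed. That is an event rate, so it cannot be the proportion of subjects with at least one event, and nothing ties it to the phase tables. Imputation in section 17 is optional and is not linked to them either.

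**The treated repeat helps.** It does, in part. Failed attempts stop before thermal delivery, so they are never in the Treated Set. A reader might infer that they dilute the treated denominator too; they do not. The repeat is optional, however, and does nothing for losses after treatment.

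**Withdrawn subjects are not all cut off at once.** A reader might infer from protocol 7.8 that all data collection stops at any withdrawal. That holds only when consent to disclosure is also withdrawn. Otherwise an Early Withdrawal visit with adverse-event monitoring is sought, and subjects who leave because of an adverse event are followed until it resolves or is stable. No continuing surveillance for new events is stated.

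**Conclusion.** The point holds. Under the stated rule, Year 1 and especially Year 2 subject rates fall below the risk among observed subjects as follow-up is lost. On the treated denominator the relative understatement equals the loss fraction if every loss precedes the phase. It is smaller if losses are spread: about 1.5, 3.0 and 4.4 points on a 20% Year 2 risk at 10%, 20% and 30% loss. On the enrolled denominator the dilution is larger, up to a further factor of 0.667 if 45 are enrolled for 30 treated. That factor may be smaller in practice, because the 45 belongs to a SAP written against Rev A.

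Three limits apply. The documents state no loss rate, so the size is illustrative. The denominator is read from the defined term and the opening of SAP 11.1.1; the Phase paragraph does not restate it. The direction assumes that loss is unrelated to adverse-event risk.

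A reader might infer that drop-out alone must push the Year 2 rate below the Year 1 rate. The documents do not support that: Year 2 is 30 days longer, and at a constant daily hazard with 10% loss Year 2 reads 18.5% against 17.9% for Year 1. The reversal does appear at 20% and 30% loss.

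**What to change.** In SAP 11.1.1:

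1. For the Operative, Year 1 and Year 2 phases, use as denominator the subjects still in the study on the first day of the phase (start of procedure, day 31, and the day after 12 study months), and print that number in the table. Failed attempts count in the Operative phase only.
2. Add events per subject-time of observation, following SAP 12.4 and ended at study exit, and say that 12.4 applies to these tables. This removes the within-phase residual and allows for the unequal phase lengths.
3. For combined phases such as Operative through Year 2, add a Kaplan-Meier estimate of time to first event, censored at exit.
4. Keep the all-enrolled proportion as a supplement.

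The cost is SAP wording and some extra programming, and later-phase rates will look slightly less favourable. Confirm that the exit date is captured: protocol 7.8 says the Study Completion form records the reason for discontinuation but does not mention a date. Bias from withdrawal related to adverse-event risk is not fully removed. If higher-risk subjects leave, an at-risk denominator also understates, so the reasons for withdrawal should be shown next to the phase tables.
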